### ***Protocol Title***

Transabdominal Ultrasound with BR55 for Characterization of Pancreatic Lesions

### ***Protocol No.***

This study is being conducted under protocol number: BR55-110.  
IND number: 114,098.

### ***Objectives***

The objectives of this exploratory study are:

- to assess the ability of BR55 contrast-enhanced ultrasound (CEUS) to characterize pancreas lesions using transabdominal ultrasound (US) in subjects with suspected pancreatic ductal adenocarcinoma (PDAC) on the basis of a visual score (semi quantitative visual assessment of BR55 enhancement) using histopathology as the truth standard (TS);
- to expand the safety profile of BR55 in subjects with suspected pancreatic cancer.

Additional exploratory objectives of the study are:

- to correlate the signal intensity (SI) of the target lesion on BR55 CEUS with lesion type (malignant or benign) as determined by histopathology;
- to assess the correlation between SI of the target lesion on BR55 CEUS and VEGFR2 expression as determined by IHC;
- to assess the correlation between SI of the target lesion on BR55 CEUS and microvessel density (MVD) as determined by IHC.

### ***Investigational Plan***

This is an exploratory, single center, open label, parallel-dose, and prospective study of BR55 CEUS for characterization of solid pancreatic lesions in subjects with suspected PDAC using transabdominal US. This study will be conducted in the US.

Approximately twenty-four (24) subjects with suspected PDAC and scheduled to undergo surgical resection or endoscopic ultrasound-guided fine needle biopsy (EUS-FNB) within 30 days (but not before 24 hours) after the transabdominal BR55 CEUS examination will be enrolled.

Subjects will be enrolled into 3 dose groups starting with the lowest dose group as follows:

- Dose group 0.03mL/kg
- Dose group 0.05mL/kg
- Dose group 0.08mL/kg

A maximum of 8 patients will be enrolled in each dose group according to the following methodology.

Enrollment into the next higher dose group will be based on the technical adequacy of the ultrasound acquisitions, as determined by a consensus medical review of images acquired in the first 4 subjects of the preceding dose group. Technical inadequacy of the ultrasound acquisitions will be determined in accordance with, but not limited to the following criteria:

- absent or insufficient contrast enhancement during the wash-in phase
- absent or insufficient contrast enhancement in subsequent image acquisitions (i.e. after the wash-in phase)
- lack of visualization of the target lesion in the post-contrast image acquisitions

Efficacy evaluations will be made on the US images that are acquired adequately. The Investigator will record the size, location and echogenicity of the lesion for UEUS. After BR55 is administered, the CEUS images will be evaluated for contrast enhancement using a semi-quantitative scale and a quantitative measurement of the SI in the target lesion vs. surrounding pancreatic tissue.

The final cancer diagnosis will be obtained for all subjects by histopathology.

Safety will be evaluated in this study by performing physical exams, collecting concomitant medications and the monitoring of adverse events, vital signs, electrocardiograms, laboratory tests and pulse oximetry.

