**Final Version**  
**10 April 2019**

---

Three different doses of BR55 will be evaluated: 0.03, 0.05 and 0.08 mL/kg. A total of eight (8) subjects will be enrolled sequentially into each dose group starting at 0.3 ml/kg.

A maximum of 8 patients will be enrolled in each dose group according to the following methodology.

Enrollment into the next higher dose group will occur either after a total of 8 subjects complete enrollment, or the first 4 subjects enrolled in the previous dose group have CEUS images that are not technically adequate based on consensus medical review by PI & Bracco. Reasons for technical inadequacy will be recorded on the CRF and may include the following:

- absent or insufficient contrast enhancement during the wash-in phase
- absent or insufficient contrast enhancement in subsequent image acquisitions (i.e. after the wash-in phase);
- lack of visualization of the target lesion in the post-contrast image acquisitions

In each subject, the administration of BR55 will be followed by a 10 mL 0.9% saline flush.

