### Electrocardiograms

Acquire a 12-Lead ECG within 2 hours prior to and at approximately 30 min, 1 hour and 24 hours after BR55 administration. Attach a photocopy of the ECG report to the appropriate page of the Case Report Form.

ECG examinations will be performed locally and the ECG reports will be evaluated by a local cardiologist.

*Imaging Procedures*Ultrasound Equipment

The transabdominal UEUS and CEUS examinations will be performed with FDA-approved ultrasound equipment, commercially available for clinical applications. The BR55 CEUS evaluation of the pancreas should be performed with a contrast dedicated platform and equipped with a multi-frequency curved array transducer used for conventional transabdominal US examinations.

For standardization purposes, the same ultrasound system and transducer will be used for all subjects enrolled at the investigational site. Additionally, any technical interventions (including software release updates and periodic system maintenance) will be evaluated by the Sponsor in order to make sure the image quality is not affected.

A study dedicated preset will be installed on the selected ultrasound machine.

Ultrasound Image Acquisition

A detailed description of both the UEUS and BR55 CEUS acquisition protocols will be provided in a dedicated Imaging Manual.

The BR55 CEUS examination of the pancreas must be preceded by a standardized transabdominal UEUS examination of the pancreas to identify the focal target lesion. Oral fluid may be administered as needed to reduce shadowing gas in the stomach. Optimally, it should be possible to view the entire lesion within the field of view of the ultrasound transducer. UEUS will also serve to identify the optimal plane for imaging the target lesion after BR55 administration.

For the subsequent BR55 CEUS, to prevent microbubble destruction, the procedure should be performed in contrast mode using a low Mechanical Index.

Contrast inflow into the target lesion will be observed in the optimal imaging plane for approximately 60 seconds and using a low frame rate. Post-contrast images will be acquired at 2 minute time intervals, starting at 2 minutes and continue up to 30 minutes post BR55 administration, or until stationary enhancement in the lesion is no longer visible, whichever occurs first.

A copy of the DICOM images will be transferred to the Bracco Imaging Core Laboratory.

*Efficacy Evaluations*Unenhanced Ultrasound (UEUS) Assessment

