**Contrast Enhanced (CEUS) Ultrasound Assessment**

The investigator should indicate in the Case Report Form whether or not contrast enhancement was seen in the target lesion during the 60 second wash-in phase. Also the investigator should record the degree of specific (e.g., BR55-VEGFR2 binding) enhancement seen according to the 3-point semi-quantitative visual scale outlined below.

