**Visual Assessment of BR55 Enhancement of the Target Lesion**

BR55 contrast-enhanced images will be assessed by the investigator using the following semi-quantitative scale:

1. No enhancement: No focal targeted, stationary imaging signal is detectable.
2. Weak enhancement: Weak focal targeted imaging signal is detectable and considered as possibly stationary.
3. Strong enhancement: Well defined and strong focal targeted imaging signal is detectable and considered as definitely stationary.

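### Image adequacy for efficacy is undefined and follows a list counting missing enhancement as inadequate, although missing lesion enhancement is a valid result (minor)

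*Combined protocol and SAP*

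**What the plan says.** Four places in the combined protocol and SAP bear on this.

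- **Investigational Plan.** Moving to the next dose group depends on a consensus review of "images acquired in the first 4 subjects of the preceding dose group". An open list of inadequacy criteria follows: too little or no enhancement in wash-in, "absent or insufficient contrast enhancement in subsequent image acquisitions (i.e. after the wash-in phase", and failure to see the target lesion after contrast. The sentence straight after the list is "Efficacy evaluations will be made on the US images that are acquired adequately".
- **Administration.** The same three items appear again for dose progression, with the note "Reasons for technical inadequacy will be recorded on the CRF and may include the following".
- **CEUS and visual assessment sections.** The investigator records "whether or not contrast enhancement was seen in the target lesion during the 60 second wash-in phase", so wash-in enhancement is data whether present or absent. Score 1 of the visual scale is defined by "No focal targeted, stationary imaging signal is detectable".
- **Statistical Methods.** Analysis Population takes all dosed subjects with efficacy data and sets no adequacy condition. Efficacy Analysis (General) adds the word *evaluable* without defining it. The visual score is to be tabulated against histopathology with *none* as a category, and signal intensity with *no signal* as a category.

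**The concern.** One observation, a lesion that does not enhance, can be read either as a result or as a reason to set the examination aside. No sentence says which reading applies to efficacy. The only adequacy standard in the documents overlaps with the outcome being measured, and the efficacy restriction follows it directly in nearly the same words.

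The table of visual score by histopathology serves the first study objective. If examinations without enhancement were treated as inadequate, the enhancing fraction would be too high in malignant and in benign lesions, and the lowest signal-intensity category would be thinned. The study is open label, the investigator assigns the score, and the adequacy review is made by the principal investigator and the sponsor. The documents describe no blinding of that review to the score, so the rule should be fixed before scores are seen.

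**Working it through.** **The texts side by side**

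| Observation | As an inadequacy criterion (Investigational Plan, Administration) | As a result |
|---|---|---|
| No wash-in enhancement | Listed | Recorded as yes or no for the lesion (CEUS assessment) |
| No enhancement after wash-in | Listed | Score 1 (visual assessment); *none* (Efficacy Analysis); *no signal* (signal intensity vs. TS) |
| Lesion not visualized after contrast | Listed | Not a score category |

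The first two rows conflict if the list is used for efficacy. The third does not. The overlap in the second row is partial: the criterion speaks of contrast enhancement in general, while score 1 is the absence of a focal, stationary signal. A well-perfused image may still score 1 without meeting the criterion.

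**Size: illustration only**

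The documents give no enhancement rates and no visual-score cut-off. The only planned figure is enrollment: 3 groups × 8 = 24, which matches the Sample Size section.

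Assumptions:
- 20 malignant and 4 benign lesions.
- Weak or strong counts as enhancing: 14/20 malignant and 1/4 benign.
- Score-1 lesions are then 6 + 3 = 9.
- All three groups fill to 8.

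Reach of the documented review: the first 4 subjects of the two groups that precede another, 2 × 4 = 8 of 24. Expected score-1 lesions among them: 6 × 8/24 = 2 malignant and 3 × 8/24 = 1 benign, 3 in all.

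If those 3 were all dropped:
- Malignant: 14/20 = 70% (exact 95% CI 46 to 88) becomes 14/18 = 78% (CI 52 to 94).
- Benign: 1/4 = 25% (CI 1 to 81) becomes 1/3 = 33% (CI 1 to 91).
- Odds ratio: (14 × 3)/(6 × 1) = 7.0 before and (14 × 2)/(4 × 1) = 7.0 after.

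In general, with true enhancing fraction p and a share q of score-1 lesions dropped, the observed fraction is p′ = p / [p + (1 − p)(1 − q)]. With q = 3/9 = 1/3:

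| Lesion type | Assumed p | p′ |
|---|---|---|
| Malignant | 50%, 70%, 90% | 60%, 78%, 93% |
| Benign | 10%, 25%, 50% | 14%, 33%, 60% |

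The fraction rises in both lesion types whenever some score-1 lesions of that type are dropped. Removal in equal proportion leaves the odds ratio unchanged. Unequal removal of 3 could move it either way: 3 malignant and 0 benign gives (14 × 3)/(3 × 1) = 14; 1 malignant and 2 benign gives (14 × 1)/(5 × 1) = 2.8.

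**The case against.** The case for leaving the text alone is substantial.

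- **The list has another job.** It is introduced for dose progression and is expressly open. Its use for efficacy is an inference from position and similar wording. This stands, but no sentence confines the list to dose progression, and without it the efficacy restriction has no stated content in these documents.
- **The criterion is not score 1.** It does not name the lesion and can be read as failed contrast delivery or imaging. This stands and limits the number of cases at risk.
- **The analysis text leans toward retention.** Analysis Population has no adequacy condition, *none* and *no signal* are planned categories, and acquisition may normally run "until stationary enhancement in the lesion is no longer visible, whichever occurs first", so loss of signal is not in itself a failed examination. This stands as a sign of intent. It does not remove the image restriction or the undefined *evaluable*.
- **The Imaging Manual may settle it.** The plan says "A detailed description of both the UEUS and BR55 CEUS acquisition protocols will be provided in a dedicated Imaging Manual". That manual is not available here, and it may define adequacy.
- **Losses would be visible.** Reasons go on the CRF, and Data Handling has tables show missing counts. That would disclose the loss but not restore the results.

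A reader might infer that the plan orders removal of score-1 results, or that every score-1 lesion would go, which would drive apparent sensitivity to 100% and specificity to zero. The documents do not support this: nothing orders removal, the overlap is partial, and the plan calculates neither measure for the visual score. Nor do they say that a dose group judged inadequate would lose its efficacy data.

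**Conclusion.** The concern holds as a conflict between stated rules, and it is minor. The wording leaves open an exclusion that depends on the outcome; it does not require one. If that route were taken, the enhancing fraction would be overstated in both lesion types. Under the assumed rates the malignant figure moves by 8 percentage points (70% to 78%), well inside either confidence interval. The study is exploratory, its sample size has no statistical basis, and only frequency tables are planned for the visual score, so little hangs on a shift of that size. The error would nevertheless always run in the same direction, and it can be prevented with a few words. The conclusion rests on the text. The figures rest wholly on assumed rates and on every score-1 lesion within the review's reach being dropped, so they are not a forecast.

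**What to change.** In Investigational Plan and in Efficacy Analysis (General):

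1. Define adequacy for efficacy only by acquisition features that do not depend on enhancement of the target lesion: the lesion lies in the imaging plane, contrast is seen to arrive in the imaged field, and usable frames are stored. If the Imaging Manual already does this, cite it.
2. State that an adequate acquisition without late lesion signal is scored 1 and kept in all efficacy tables.
3. Delete *evaluable*, or define it to match Analysis Population.

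The dose-progression criteria in Investigational Plan and Administration must also be reconciled with the scoring scale. No progression rule is proposed here.

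The cost is wording only, with no new data or subjects. The downside for the sponsor is that the observed enhancing fraction in malignant lesions may be lower than if such cases were dropped.

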#### *Study Duration*

A subject's participation will begin at the time of signing the informed consent through the 24-hour follow-up after the administration of BR55.

The planned imaging procedures, namely the transabdominal unenhanced US and BR55 CEUS, will be completed within 60 minutes including up to 30 minutes of CEUS examination.

Safety monitoring will begin at the time of signing the Informed Consent and will continue for 24 hours after BR55 administration.

#### *Study Population*

This is a single center study including one investigative site in the United States. It is planned to enroll approximately 24 subjects with solid pancreatic lesions and suspected PDAC who are scheduled to undergo surgical resection or endoscopic ultrasound-guided fine needle biopsy (EUS-FNB) within 30 days of the BR55 CEUS examination, but not before completion of the safety assessment at 24 hours post BR55 administration.

*Inclusion Criteria*

Enroll a subject in this study if the subject meets the following inclusion criteria:

- Is at least 18 years of age;
- Has at least one solid pancreatic lesion;
- Is scheduled to undergo surgical resection or endoscopic ultrasound-guided fine needle biopsy (EUS-FNB) for suspected PDAC not earlier than 24 hours and not later than 30 days following BR55 administration;
- Provides written Informed Consent and is willing to comply with protocol requirements.

*Exclusion Criteria*

Exclude a subject from this study if the subject does not fulfill the inclusion criteria, or if any of the following conditions are observed:

- Is a pregnant or lactating female. Exclude the possibility of pregnancy:
  - by testing on site at the institution (serum  $\beta$ HCG) within 24 hours prior to the start of investigational product administration,
  - by surgical history (e.g., tubal ligation or hysterectomy),
  - by post-menopausal status with a minimum 1 year without menses;
- Has undergone prior systemic therapy for pancreatic cancer;
- Has history of concurrent malignancy;
- Has history of any clinically unstable cardiac condition including class III/IV congestive heart failure;
- Has had any severe cardiac rhythm disorders within 7 days prior to enrolment;
- Has severe pulmonary hypertension (pulmonary artery pressure  $> 90$ mmHg) or uncontrolled systemic hypertension and/or respiratory distress syndrome;
- Has open and/or non-healing wounds in the chest, abdomen and pelvis;
- Has other systemic vascular abnormalities associated with neovascularization, such as macular degeneration, that in the opinion of the investigator could significantly affect the ability to evaluate the effects of BR55;
- Is participating in a clinical trial or has participated in another trial with an investigational compound within the past 30 days prior to enrolment;
- Has previously been enrolled in and completed this study;
- Has any known allergy to one or more of the ingredients of the Investigational Product or to any other contrast media;

Final Version

[figure not shown]
10 April 2019

---

- Is determined by the Investigator that the subject is clinically unsuitable for the study;
- Has had major surgery, including laparoscopic surgery within 3 months prior to enrolment;
- Has history of pancreatic surgery (e.g., cyst removal);
- Has acute pancreatic abnormalities (acute pancreatitis or trauma).

### *Investigational Products*

The study IP is BR55.

### *Administration*

The calculated dose of BR55 will be administered by slow IV bolus injection through an angiocatheter (20G). Strict adherence to aseptic technique must be maintained and subjects will be observed throughout the procedure.

Weight measurements will be collected within 2 hours prior to BR55 administration for dose calculation.

**Final Version**  
**10 April 2019**

---

Three different doses of BR55 will be evaluated: 0.03, 0.05 and 0.08 mL/kg. A total of eight (8) subjects will be enrolled sequentially into each dose group starting at 0.3 ml/kg.

A maximum of 8 patients will be enrolled in each dose group according to the following methodology.

Enrollment into the next higher dose group will occur either after a total of 8 subjects complete enrollment, or the first 4 subjects enrolled in the previous dose group have CEUS images that are not technically adequate based on consensus medical review by PI & Bracco. Reasons for technical inadequacy will be recorded on the CRF and may include the following:

- absent or insufficient contrast enhancement during the wash-in phase
- absent or insufficient contrast enhancement in subsequent image acquisitions (i.e. after the wash-in phase);
- lack of visualization of the target lesion in the post-contrast image acquisitions

In each subject, the administration of BR55 will be followed by a 10 mL 0.9% saline flush.

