Obtain a complete medical history including disease related medical history and scheduled date for surgery for resection or endoscopic ultrasound-guided fine needle biopsy (EUS-FNB) of the suspected PDAC after the subject has signed the Informed Consent and within 24 hours prior to IP administration. Record the subject's medical history on the Medical History section of the Case Report Form.

Pregnancy Test

Exclude the possibility of subject's pregnancy:

- by testing (serum  $\beta$ HCG) within 24 hours prior to the start of investigational product administration;
- by surgical history (e.g., tubal ligation or hysterectomy);
- by post-menopausal status with a minimum of 1 year without menses

Concomitant Medications

Record all medications (prescription and over-the-counter) taken within 24 hours prior to IP administration in the Concomitant Medication section of the Case Report Form. Additionally, record newly prescribed pharmacological treatments in this section up through 24 hours post IP administration.

*Safety Assessment*Adverse Events

Monitor subjects for any untoward medical occurrences from the time of signing of Informed Consent through 24 hours post BR55 administration. Record all untoward medical events in the Adverse Event section of the CRF as specified in the protocol. Only post-dose untoward medical occurrences will be tabulated as adverse events.

All serious adverse events that occur during the study monitoring period are required to be collected regardless of the relationship to BR55 on the Serious Adverse Event Report (SAER) Form.

In addition, the investigator should report any serious adverse events that occur after the monitoring period that he/she believes may be related to the BR55 on the SAER Form.

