### Physical Examination

Perform a physical examination within 24 hours prior to and at 24 hours after BR55 administration.

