### Laboratory Evaluations

Collect blood and urine samples within 24 hours prior and at 24 hours post BR55 administration for evaluation of the analytes listed in the protocol.

A local laboratory will be utilized for analyzing and reporting laboratory results.

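### As supplied, the rule for opening the next BR55 dose group does not require the lower dose's 24-hour safety data to be complete or considered first

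*Combined protocol and SAP*

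**What the plan says.** Dose groups are filled one after another, lowest dose first, with at most eight subjects each. Two sections of the combined protocol and SAP describe how the next group opens.

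- **Administration** gives two routes. On the first, "Enrollment into the next higher dose group will occur either after a total of 8 subjects complete enrollment"; the supplied text does not define what completing enrollment means. On the second, "the first 4 subjects enrolled in the previous dose group have CEUS images that are not technically adequate based on consensus medical review" by the principal investigator and the sponsor.
- **Investigational Plan** gives one basis only, the technical adequacy of the acquisitions, "as determined by a consensus medical review of images acquired in the first 4 subjects of the preceding dose group". The three listed criteria concern enhancement or visibility of the lesion.

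Safety is one of the two main aims in the Objectives section: "to expand the safety profile of BR55 in subjects with suspected pancreatic cancer". Each subject is followed for 24 hours after dosing:

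- Adverse events (Safety Assessment): "All serious adverse events that occur during the study monitoring period are required to be collected regardless of the relationship to BR55".
- Physical Examination: "Perform a physical examination within 24 hours prior to and at 24 hours after BR55 administration".
- Laboratory Evaluations: "Collect blood and urine samples within 24 hours prior and at 24 hours post BR55 administration".
- Electrocardiograms: "the ECG reports will be evaluated by a local cardiologist".
- Vital Signs: taken at 30 minutes, 1 hour and 24 hours after the injection.

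**The concern.** The safety data are collected, but nothing ties them to the decision to raise the dose. The only review described as governing that decision is a review of images. A group could therefore open because eight subjects have been entered, or because four sets of images were poor, with no record that the lower-dose safety findings supported the step.

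Serious events would probably reach the sponsor through their own reporting route. The exposed part is the non-serious adverse events and the laboratory, ECG and vital-sign changes. A pattern in these may show only when the subjects of a group are looked at together, and the stated rule does not ask for that before a higher dose is given.

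**Working it through.** **1. The plan's own total.** The Investigational Plan and Sample Size sections give about 24 subjects in three groups, with at most 8 per group: 3 × 8 = 24. The figure is reproduced. The plan says that it has no statistical basis, so there is no power calculation to check.

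**2. Search for a safety condition on the dose step.**

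| Section | What it contributes | Makes the step depend on safety data? |
|---|---|---|
| Investigational Plan | Image adequacy in the first four subjects. The list of reasons is open-ended, but it is a list of reasons for technical inadequacy. | No |
| Administration | Eight subjects entered, or inadequate images in the first four | No |
| Study Population | The subject's own surgery or biopsy must wait for that subject's 24-hour safety assessment | No, but it shows the plan already uses this kind of condition |
| Safety Assessment to Electrocardiograms | Collection for each subject, with ECGs read by a cardiologist | No |
| Safety Analysis | Summary tables | No |
| Interim Analyses | None planned | No |

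The last two rows carry little weight on their own. A clinical check before a dose step is neither a final table nor an interim statistical analysis.

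**3. Size of the steps.** 0.05 / 0.03 = 1.67 (+67%); 0.08 / 0.05 = 1.60 (+60%); overall 0.08 / 0.03 = 2.67-fold. Subjects dosed after a step: at most 8 + 8 = 16 of 24.

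**4. Monitoring still outstanding when the last subject's imaging ends.** Follow-up lasts 24 hours (Study Duration). Imaging runs to 30 minutes, or stops sooner if stationary enhancement is no longer visible (Ultrasound Image Acquisition). With imaging ending at t ≤ 0.5 h, the time outstanding is 24 − t ≥ 24 − 0.5 = 23.5 h. This is a minimum: it is longer when imaging stops early, as is likely when enhancement is absent.

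**5. What a look at 4 or 8 subjects could detect.** The true event rates p are assumptions for illustration; the documents give none. The chance of at least one event is 1 − (1 − p)^n.

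| Assumed p | n = 4 | n = 8 |
|---|---|---|
| 10% | 1 − 0.9^4 = 34% | 1 − 0.9^8 = 57% |
| 20% | 1 − 0.8^4 = 59% | 1 − 0.8^8 = 83% |
| 30% | 1 − 0.7^4 = 76% | 1 − 0.7^8 = 94% |

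With no events seen, the one-sided 95% upper limit for the rate is 1 − 0.05^(1/n): 53% for 0/4 and 31% for 0/8. Such a check can catch common effects but not rare ones.

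**The case against.** **The rule may be elsewhere.** The supplied text defers to the protocol for recording adverse events, for the list of laboratory analytes and for the follow-up period. Holding and stopping rules could sit there too. This stands. The finding is about the text as supplied and does not show that the study has no such rule.

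**Completing enrollment may mean completing participation.** Study Duration runs participation through the 24-hour follow-up. On that reading the eight-subject route already needs complete data. It still would not require anyone to consider them, and the four-subject route, which moves up on the fewest subjects, would have no safety condition at all.

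**This is an imaging study of an agent already given to people.** The aim of expanding a safety profile implies earlier human exposure, and the stated reasons for moving up concern imaging. This also stands, and it limits the importance of the point. The documents do not say which doses were given before. If 0.05 and 0.08 mL/kg were among them, the check would mainly be confirmation in this population.

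**Safety is already watched.** A reader might infer from the dose rule that safety goes unmonitored, or that subjects would be harmed. The documents do not support either. Serious events are collected, ECGs are read by a cardiologist, and the investigator at the only site takes part in the image consensus. The +67% and +60% are dose ratios, not evidence of risk.

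**The 23.5 hours may never arise in practice.** A reader might infer that the next dose follows at once when imaging ends. The documents do not say so. The next subject's pre-dose assessments come first, as does the image consensus on the four-subject route, and incomplete data would usually concern only the last subject or few. On the eight-subject route, however, no review is described after the eighth subject.

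**Conclusion.** The point holds in a narrow form. As supplied, neither statement of the dose-step rule requires the lower dose's 24-hour safety data to be complete or considered before a +67% or +60% increase, which at most 16 of 24 subjects follow. What is missing is a joint look at non-serious adverse events and laboratory, ECG and vital-sign data before the step, with the decision recorded.

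The importance is modest and confidence is moderate. Both rest on two things the documents do not settle: whether the full protocol contains such a rule, and whether the two higher doses have been given to people before. The undefined enrollment term and the mismatch between the two sections are drafting matters. They need correcting but do not make the safety point more serious. The change is still worth making, because it is cheap and the data are already being collected.

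**What to change.** State one rule, in the same words, in the Investigational Plan and Administration sections. The first subject at the next dose is dosed only after:

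1. eight subjects in the current group have been dosed, or the first four subjects' images have been found not technically adequate;
2. on either route, all subjects dosed in the current group have completed the 24-hour safety assessment; and
3. the principal investigator and the sponsor have reviewed those subjects' adverse-event, laboratory, ECG and vital-sign data and filed a dated go or hold decision.

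This replaces the undefined enrollment term. The sponsor's clinical team should write down beforehand which findings lead to a hold. If the full protocol already has an equivalent rule, a cross-reference in both sections is enough.

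**Cost.** There is no change in sample size, and the data and reviewers are the same. On the four-subject route the safety review is added to the existing image consensus. On the eight-subject route it is a new, short review by the same people. The data must be compiled for each review and the hold criteria drafted. Each step waits at least 24 hours after the last lower-dose injection, plus turnaround. The documents give no turnaround time. Assuming 1 to 4 days, the delay is 1 + 1 = 2 to 1 + 4 = 5 days per step, or 4 to 10 days over two steps.
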